6.4 Sample size calculation

The initial sample size calculation was based on our primary hypothesis and primary study outcome. The required sample size was calculated using data from a multicenter randomized controlled trial reporting intubation rate in patients with acute hypoxemic respiratory failure with a PaO₂/FiO₂ ratio less than 200 using HFNC²⁵.

These calculations indicated that 322 patients would be required per group, assuming a twosided significance level of 0.05 and a power of 80%, to detect the expected difference in the

rate of mechanical ventilation between the prone position group of 24 % and the standard treatment group of 34 % (risk ratio of 0.70). Assuming a dropout rate of 10%, **a total of 714 patients** (n= 357 per group) were planned to be included in the study.

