8. STATISTICAL ANALYSIS

8.1 Descriptive statistics

Patient characteristics will be compared and described by appropriate statistics.

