8.2 Analysis

The goal of the primary outcome is to quantify the effect of prone position versus the standard treatment upon the need for invasive mechanical ventilation during the first fourteen days after randomization.

Interim analyses for efficacy and futility will be conducted at 50% (N= 357), 75% (N= 476), and 100% (N= 714) of the planned enrollment, as needed, using a non-binding group sequential design with gamma spending functions (gamma = -4 for each of alpha and beta).

The table below shows the alpha and beta spent over the trial, z-statistic boundaries for efficacy and futility, and boundary-crossing probabilities under the alternative hypothesis (H1). The corresponding P-value boundaries for efficacy (futility in parentheses) at the 1st, 2nd and final looks, respectively, are P≤ 0.006 (P>0.82), P≤ 0.015 (P>0.35), and P ≤ 0.044 (P>0.044). The Figure below displays the z-statistic boundaries for efficacy/harm and futility as a function of accrued sample size.

For the primary efficacy analysis rates of invasive mechanical ventilation will be compared between the two intervention groups, and the odds ratio relative risks with corresponding 95% confidence levels interval will be calculated using logistic regression analysis.

With regard to the remaining parameters: Normally distributed variables will be expressed by their mean and standard deviation; non-normally distributed variables will be expressed by their medians and interquartile ranges. Categorical variables will be expressed as n (%).

Student's t-test will be used to test groups of continuous normally distributed variables.

Conversely, if continuous data is non-normally distributed, the Mann-Whitney-U test will be used. Categorical variables will be compared with the Chi-square test, Fisher's exact tests, or, where appropriate, as relative risks. Time-dependent data will be analyzed using a proportional hazard model adjusted for possible imbalances of patients' baseline characteristics.

COVID-19 status of patients will be taken into account and analyzed in the study to find any

differences in the primary and secondary outcomes between COVID-19 and non-COVID-19 patients.

A stratified analysis will be done by the device used (HFNC, BIPAP, CPAP, and their interfaces).

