The statistical analysis will be based on the intention-to-treat principle. Besides, we will perform a per-protocol analysis to check for the robustness of the results. The intention-to-treat analysis includes all patients as randomized regardless of whether they received the randomized treatment or other protocol deviations. Per-protocol group analysis only considers those patients who completed the treatment according to the originally allocated protocol.

Data analyses will follow an a priori documented statistical analysis plan, which will be finalized before the end of data collection. By definition, only the analysis of the primary outcome is confirmatory; all other analyses are exploratory. The analysis strategy follows the intention-to-treat principle. The analysis will be undertaken blinded by a statistical expert. Statistical significance is considered to be at a p-value of 0.05, where 95% confidence levels will express appropriate statistical uncertainty.

The analysis will be performed with R statistics.

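### The proportional hazards model adjusts for baseline imbalances rather than for pre-specified prognostic covariates; this affects only the exploratory time-to-event analyses and costs power, not validity

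*Protocol*

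**What the plan says.** Protocol section 8.2, in the part dealing with outcomes other than the primary, states that time-dependent data will be "analyzed using a proportional hazard model adjusted for possible imbalances" in baseline characteristics. It names no covariate, no prognostic criterion and no definition of imbalance. Section 8.1 adds: "Patient characteristics will be compared and described by appropriate statistics".

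Four other statements set the limits of the point, all from section 8.2:

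- The primary endpoint has its own analysis, in which the effect estimate and its "interval will be calculated using logistic regression analysis". No imbalance adjustment is attached to it.
- On status, "only the analysis of the primary outcome is confirmatory; all other analyses are exploratory".
- On pre-specification, "Data analyses will follow an a priori documented statistical analysis plan, which will be finalized before the end of data collection".
- On blinding, "The analysis will be undertaken blinded by a statistical expert".

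Section 7.2.4 lists the baseline variables to be collected, including age, SpO2/FiO2, ROX index, SOFA and type of respiratory support. Section 7.2.1 says that randomization is central, 1:1 and balanced per centre.

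**The concern.** With valid randomization, baseline differences between arms are chance, and which ones occur is known only from the data. A rule keyed to imbalance therefore lets chance choose the model. A strong predictor that happens to be balanced is left out, and an irrelevant variable that happens to differ goes in. The protocol fixes this as its selection principle, so it is more than a detail left to the SAP: an SAP that follows the sentence inherits the rule, and one that does not departs from the protocol.

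At stake are the calibration and power of any adjusted hazard ratio, and how far a reader can trust that the covariates were not picked with the result in view.

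**Working it through.** **1. The plan's own figure.** Section 6.4 assumes 34% versus 24%, with a two-sided "significance level of 0.05 and a power of 80"%. With pooled variance under the null:

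n = [1.96·√(2·0.29·0.71) + 0.8416·√(0.34·0.66 + 0.24·0.76)]² / 0.10² = (1.2578 + 0.5368)² / 0.01 ≈ 322.05

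This is 323 per group rounded up, against 322 stated. Allowing for 10% dropout, 322/0.9 = 357.8, against 357 stated. The figure reproduces within rounding. The protocol gives no figure for the proportional hazards model.

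**2. The survival-scale equivalent.** The implied hazard ratio is ln(0.76)/ln(0.66) = 0.66. Expected events in 714 patients are 357 × (0.34 + 0.24) = 207.

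**3. Simulation.** There were 357 patients per arm, exponential event times censored at day 14, and a control risk of 34%. The test was a two-sided Wald test at 1.96 in a Cox model. There were 15,000 runs under no effect and 4,000 at a conditional hazard ratio of 0.66. Covariates were independent standard normal, all prognostic; their number and strength are assumptions, since the protocol gives none. The imbalance rule adjusted only for covariates whose arm means differed at P<0.05 or P<0.10; these thresholds are also assumptions.

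| Covariates (log HR per SD) | Adjustment | Type I error, % | Power, % |
|---|---|---|---|
| 1 at 0.5 | none | 4.9 | 81.8 |
| | imbalance, P<0.05 | 4.6 | 81.8 |
| | imbalance, P<0.10 | 4.5 | 81.9 |
| | pre-specified | 5.0 | 84.6 |
| 5 at 0.4 | none | 5.0 | 75.2 |
| | imbalance, P<0.05 | 4.4 | 76.3 |
| | imbalance, P<0.10 | 4.1 | 77.2 |
| | pre-specified | 5.2 | 86.2 |
| 5 at 0.6 | none | 5.0 | 61.2 |
| | imbalance, P<0.05 | 4.0 | 62.4 |
| | imbalance, P<0.10 | 3.7 | 63.4 |
| | pre-specified | 5.1 | 85.5 |

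The Monte Carlo standard error is √(0.05·0.95/15,000) = 0.18 points for type I error and at most √(0.25/4,000) = 0.79 points for power. A separate check moved power from about 77% to 81% with one assumed covariate and from about 78% to 85% with four.

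**4. Where the power comes from.** In 300 simulated Cox trials per scenario, the mean standard error of the log hazard ratio was 0.1405 unadjusted and 0.1407 adjusted (one covariate at 0.5 per SD), and 0.1407 and 0.1414 (four at 0.3 per SD). Adjustment did not reduce it. The approximation 2/√207 = 0.139 agrees.

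With a standard error of about 0.14, the power figures can be turned back into hazard ratios, roughly, as exp[−0.14·(1.96 + z_power)]:

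- One covariate: unadjusted exp[−0.14·(1.96 + 0.907)] = 0.67; pre-specified exp[−0.14·(1.96 + 1.019)] = 0.66.
- Five at 0.6: unadjusted exp[−0.14·(1.96 + 0.284)] = 0.73; pre-specified exp[−0.14·(1.96 + 1.057)] = 0.66.

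The unadjusted model estimates a hazard ratio nearer 1, and the adjusted model estimates the conditional one. The stronger the omitted predictors, the wider the gap.

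**5. Favourable selection.** If an analyst could keep whichever of the unadjusted and fully adjusted results was more extreme, type I error in the three scenarios would be 6.5%, 7.6% and 8.4%.

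**The case against.** The strongest reply is that little depends on this sentence. The confirmatory analysis is the logistic regression, everything else is declared exploratory, and no endpoint in section 7.1 is labelled time-to-event, so it is unclear how much the model will be used. An SAP is promised and may name covariates, and the analyst is blinded. All of this stands, and it caps the severity. It does not make the selection principle sound. Data collection runs to day 90, so an SAP finalized just before it ends could follow complete baseline data, and coded arm labels are enough to show an imbalance. It could also be said that the sentence means anticipated imbalances, but observed ones are the more natural reading.

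A reader might infer four stronger things that the documents do not support:

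- **That false positives are inflated.** Applied mechanically, the rule errs on the safe side. The 6.5% to 8.4% needs free choice of the better result, which the blinded analysis and the a priori SAP limit.
- **That precision is wasted.** In a linear model adjustment shrinks the standard error; in this Cox model it does not (step 4).
- **That a spurious trigger is nearly certain.** Section 7.2.4 lists about 34 baseline variables besides the admission dates, and 1 − 0.95^34 = 0.825. But the protocol states no P<0.05 trigger, section 8.1 does not say that arms will be significance-tested, and the variables are not independent: ROX is computed from SpO2/FiO2 and respiratory rate.
- **That the primary result is at risk.** Section 8.2 attaches the imbalance rule only to time-dependent data.

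**Conclusion.** The point holds as a fault in a stated method, of minor to moderate weight. Choosing covariates by imbalance gives a slightly conservative test and, at P<0.05, almost none of the benefit of adjustment. A pre-specified prognostic set holds about 5% and gains about 3 to 4 points of power with one moderate covariate. With several covariates the gain ran from about 7 points (four) to 24 points (five strong ones).

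These sizes rest on assumed prognostic strengths, independent covariates, an assumed imbalance threshold and an effect fixed on the conditional scale. They show direction and rough order, not this trial's actual power. The five-strong-covariate case is an upper illustration. The conclusion about the selection principle needs none of these assumptions.

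**What to change.** In section 8.2, strike the imbalance criterion and say instead that the proportional hazards model adjusts for a short set of prognostic baseline covariates named in the SAP. The data are already collected under section 7.2.4: for example age, SpO2/FiO2 or the ROX index (one of the two, since the second contains the first), SOFA, and respiratory support device at randomization. Centre should be taken into account because randomization is balanced per centre. With about 35 centres and 207 events, roughly 6 events per centre, the SAP should say how.

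Add three short statements: the set is fixed before any between-arm baseline comparison is seen; baseline comparisons are descriptive and do not choose covariates; and the hazard ratio is conditional on the named covariates and reported as such.

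The cost is a small wording change and no new data. The one downside is that the adjusted hazard ratio is a conditional quantity and must be presented so that it is not confused with an unadjusted one.

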7. METHODS

7.1 Study parameter/endpoints

7.1.1 Main study parameters/endpoint

• Rate of invasive mechanical ventilation during the first fourteen days of enrolment

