7.2.2 Prone position

Supine to Prone

The patient will be placed in the prone position for at least 2 hours, which may be prolonged if the patient is comfortable or interrupted if the patient presents any criteria for prone position discontinuation (APPENDIX iii).

During the maneuver, FiO_2 will be increased by 25% above the baseline and then gradually decreased to the baseline value within the first 10 minutes of prone positioning, targeting for a SpO₂ of 94-96%. The total time of the prone position will be recorded.

The maneuver will be performed by two operators and the attending physician, while in patients with impaired mobility, up to 5 operators will be required. Skin protections will be used to avoid pressure sores. Also, the application of cushions will enhance patient tolerance to the

maneuver.

Arms can be at the side, in swimmer position, and can be moved to the patient's comfort. Vitals, SpO₂, and SpO₂/FiO₂ will be measured before and at the end of the prone position session.

Enteral or oral feeding will be interrupted 1 hour before prone positioning and re-established when the patient is in the semi-recumbent supine position.

Opiates, benzodiazepines, or alpha-2-adrenoceptor agonists can be used during the maneuvering at non-sedative doses to enable adaptation to the maneuver or treat anxiety symptoms related to respiratory failure.

If non-tolerance to the prone position, all clinical data will be collected, and the patients will be promptly rotated in the supine position. The reasons for prematurely unproning the patient will be accurately recorded. In case of sudden worsening of the oxygenation impairment or hemodynamics, 100% FiO₂ will be set, and the patient will be promptly positioned in the supine semi-recumbent position.

Prone to Supine

After the prone position period, the patient will be rotated to the semi-recumbent supine position for at least 2 hours and a maximum of 4 hours. This 2-hour time frame will depend on nursing availability, need for hygiene, complementary explorations, or diet.

As described previously, for the procedure, FiO_2 will be increased up to 25% above the baseline and then gradually decreased to the baseline value within the following 10 minutes targeting a SpO₂ of 94-96%.

Vitals, SpO_{2} , and SpO_{2}/FiO_{2} will be measured before and at the end of the supine position session.

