7.2.4 Data to be collected

The documentation of the data will adhere to the timetable in APPENDIX v.

Pre-randomization variables

Pre-randomization variables will be collected:

- Gender and age; female + years
- Height and weight; kg + cm
- Date and time of hospital admission
- Source of admission to the ICU (emergency department, hospital ward, transfer from another ICU, transfer from a non-ICU ward of another hospital)
- Date and time of ICU admission
- Type of non-invasive respiratory support (HFNC, NIV, CPAP)
- COPD with inhalation therapy and/or steroids
- Smoking status; never, former (at least three months prior) or current
- History of active cancer; if yes, specify the type of cancer
- History of diabetes mellitus; oral medication or insulin therapy
- History of hypertension
- Use of angiotensin-converting enzyme inhibitor
- Use of angiotensin II receptor blocker
- Use of statins
- Actual organ function evaluation
 - Respiratory rate
 - SpO₂; %
 - SpO₂/FiO₂
 - ROX index; SpO₂/FiO₂: RR
 - Dyspnea defined according to Borg dyspnea scale
 - Chest X-ray

- Non-invasive mean arterial pressure; mmHg
- Heart rate; BPM
- Body temperature; °C
- BUN, Creatinine, AST, ALT, Bilirubin, Hemoglobin, Platelets, PTT, WBC count
- SOFA score
- APACHE II, SAPS II; any of those used by the participating center

Post-randomization variables

One hour before each position change (supine and prone), the following variables will be collected for the duration of the protocol, which will be for 48 hours (APPENDIX v):

- Organ function evaluation:
 - Respiratory rate
 - SpO₂; %
 - SpO₂/FiO₂
 - ROX index; SpO₂/FiO₂: RR
 - Dyspnea defined according to the Borg dyspnea scale (APPENDIX v)
 - Non-invasive mean arterial pressure; mmHg
 - Heart rate; BPM
- Non-invasive support device parameters:
 - HFNC: flow; liters/min. FiO₂; %
 - CPAP: PEEP; cmH₂O. Flow; liters/min; Tidal volume; ml. FiO₂; %
 - NIV: PEEP; cmH₂O. Pressure support over PEEP; cmH₂O. Flow; liters/min. Tidal volume; ml. FiO₂; %
- Complications possibly related to prone position:
 - New hypotension (BPsys < 90mmHg or BPsys drop > 10mmHg, if BPsys < 90 before the maneuver)
 - New bradycardia (HR <50bpm or HR drop > 20%, if HR < 50 before the maneuver)
 - New hypoxemia (SpO₂ ≤ 90% or SpO₂ drop > 5%, if SpO₂ < 90% before the maneuver)
 - Ulcers
 - Displacements of any of the following: respiratory support device, peripheral or venous central line, oro or nasogastric tube, urinary catheter

Post-protocol variables

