APPENDIX iii. PRONE POSITION DISCONTINUATION (ANY OF THE FOLLOWING)

- Occurrence of contraindications (see APPENDIX i)
- Worsening of dyspnea according to the Borg scale after 15 minutes
- Drop in SpO₂ <90% after 15 minutes
- Nausea/vomiting
- BPsys < 90mmHg or BPsys drop > 10mmHg, if BPsys < 90 before the maneuver

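### The per-protocol set keeps only patients who completed treatment, so early intubation, the primary event, can remove a patient from the analysis meant to check the intention-to-treat result

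*Protocol*

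**What the plan says.** Section 8.2 of the protocol bases the analysis on intention to treat and then adds: "we will perform a per-protocol analysis to check for the robustness of the results". The set is defined in one sentence: "Per-protocol group analysis only considers those patients who completed the treatment according to the originally allocated protocol". The section also states that "only the analysis of the primary outcome is confirmatory; all other analyses are exploratory".

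Four other places determine what that sentence does:

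- Section 7.1.1 gives the primary endpoint: "Rate of invasive mechanical ventilation during the first fourteen days of enrolment".
- Section 7.2.4 fixes the protocol period; data are collected "for the duration of the protocol, which will be for 48 hours".
- Section 7.2.2 describes prone sessions of at least two hours that may be prolonged, or "interrupted if the patient presents any criteria for prone position discontinuation". Appendix iii lists those criteria, among them "Worsening of dyspnea according to the Borg scale after 15 minutes", a fall in SpO2 below 90%, low blood pressure, nausea or vomiting, and a new contraindication.
- Section 7.2.3 leaves standard management to each center's own practice.

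The protocol has no rule that keeps a patient intubated before 48 hours in the per-protocol set.

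**The concern.** The 48-hour treatment period lies inside the 14-day outcome window. Section 4.1 defines the patients under study as those not on invasive ventilation, so intubation ends awake proning. One event is thus both the primary outcome and a reason for not completing treatment, and a set restricted to completers is chosen partly on the outcome it is used to compare.

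The arms are also unlike each other. The prone arm has sessions to carry out and criteria for stopping them. Those criteria share a marker with the intubation criteria: SpO2 below 90% appears in both Appendix ii and Appendix iii. Prone non-completers can therefore be expected to include more patients who are intubated later. Usual care has no comparable course to complete.

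What is at stake is how the trial is read. A biased per-protocol result could appear to corroborate a chance intention-to-treat finding. After a null intention-to-treat result, it could suggest that proning works in those who tolerate it.

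**Working it through.** **Inputs from the protocol (section 6.4).** Control rate 34%, prone rate 24%, 322 per group, 357 per group after 10% dropout. These figures hold up: the pooled two-proportion formula at two-sided 0.05 and 80% power gives 323 per group, power at 322 is 80.0%, and 322/0.9 = 357.8. The planned risk ratio is 0.24/0.34 = 0.71. The protocol gives no figure for the per-protocol analysis.

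**Assumed inputs.** The protocol gives no timing of intubation and no rate of non-completion, so four loss fractions are varied:

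- f: share of prone patients with the event who are dropped
- g: share of prone patients without the event who are dropped
- h: share of control patients with the event who are dropped
- k: share of control patients without the event who are dropped

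**Formulas.** Assume no true effect, with p = 0.34 in both arms.

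- Prone per-protocol rate = p(1−f) / [p(1−f) + (1−p)(1−g)]
- Control per-protocol rate = p(1−h) / [p(1−h) + (1−p)(1−k)]
- Odds ratio = (1−f)(1−k) / [(1−g)(1−h)]

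The odds ratio shows what sets the direction. With no control losses, proning is favoured whenever f exceeds g. Control losses with h above k push the other way.

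**Two cases in full.**

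- f = 0.25, nothing else lost: 0.255 / (0.255 + 0.660) = 27.9%, and 27.9/34.0 = 0.82. This removes 357 × 0.34 × 0.25 ≈ 30 patients from the prone arm.
- f = 0.25, g = 0.10: 0.255 / (0.255 + 0.594) = 30.0%, and 30.0/34.0 = 0.88. A further 357 × 0.66 × 0.10 ≈ 24 patients are removed.

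**Range.**

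| f | g | h | k | Prone | Control | Risk ratio |
|---|---|---|---|---|---|---|
| 0.10 | 0 | 0 | 0 | 31.7% | 34.0% | 0.93 |
| 0.25 | 0 | 0 | 0 | 27.9% | 34.0% | 0.82 |
| 0.25 | 0.10 | 0 | 0 | 30.0% | 34.0% | 0.88 |
| 0.50 | 0 | 0 | 0 | 20.5% | 34.0% | 0.60 |
| 0.50 | 0.25 | 0 | 0 | 25.6% | 34.0% | 0.75 |
| 0.30 | 0.30 | 0 | 0 | 34.0% | 34.0% | 1.00 |
| 0.30 | 0 | 0.30 | 0 | 26.5% | 26.5% | 1.00 |
| 0.30 | 0.10 | 0.50 | 0.10 | 28.6% | 22.3% | 1.29 |

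**Two reference points.** If only prone events are lost, f of about 0.39 gives 24.0% against 34.0%, which is the whole planned effect with no true benefit. With f = 0.30, the chance of a two-sided P below 0.05 favouring proning is 56% when no non-events are lost and 31% when g = 0.10. Without selection it is 2.5%.

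**The case against.** A reader might infer that the selection acts in the prone arm only and makes the analysis favour proning by construction. The documents do not support that.

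- **Both arms.** The section 8.2 rule refers to the allocated protocol of either arm. Section 7.2.5 gives the 48-hour protocol end to both groups, and the Appendix v timetable records protocol dropout for randomized patients without limiting it to one arm. A control intubated early could also be dropped.
- **Permitted stops.** Section 7.2.2 makes interruption under Appendix iii part of the allocated protocol and lets the patient choose to stay supine in the evening. A patient stopped in this way can be read as treated according to protocol.
- **Size.** A risk ratio of 0.60 requires half of the prone events to be lost and no one else in either arm. Some stop criteria, such as vomiting, need not lead to intubation, so some non-events would probably be lost too.
- **Status.** Intention to treat is the basis, other analyses are exploratory, and a statistical analysis plan that is not shown may define completion.

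All of this limits the claim about direction and size. It does not remove the core. The plain wording still excludes a prone patient intubated before 48 hours, and the protocol states that rule rather than leaving it open. If both arms lose early events equally, the null bias disappears, but the analysis then discards early primary events and any early effect with them. It would still not be a check on the intention-to-treat result.

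**Conclusion.** The point stands as one that should be fixed. As worded, the per-protocol set is selected on the primary outcome and is not a valid robustness check. Bias toward proning is the likely direction, because only that arm has sessions and stop criteria to complete, but it is not certain.

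If only prone patients are lost, and events are lost more often than non-events, the null risk ratio runs from 0.93 down to 0.60 over the cases shown. It is 1.00 under equal losses and 1.29 in the crossover case. All these values rest on assumed loss fractions and on 34% intubation in both arms. The protocol does not allow one to be chosen.

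The confirmatory intention-to-treat analysis is untouched. The harm is false reassurance, or a false signal, from a secondary analysis.

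**What to change.** Replace the defining sentence in section 8.2 with a short paragraph that does the following:

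1. Assess adherence by the same rule in both arms, and only up to the earliest of intubation, death, a protocol-permitted stop, or 48 hours.
2. Keep every patient who followed the allocation up to that point, and count early intubation as an outcome, not as non-completion.
3. Exclude only patients who never started the allocated management or who crossed over.
4. Describe the analysis as exploratory and still open to selection, and do not present it as confirming the intention-to-treat result.

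A complier-average analysis with allocation as the instrument is optional. It would need a stated definition of compliance, since sessions vary in number and length, and its assumptions, including the exclusion restriction, would have to be set out.

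The cost is one paragraph. Total prone time and the reasons for early return to supine are already recorded under section 7.2.2, and protocol dropout is in the Appendix v timetable. No clinical rule changes.

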7.2.1 Randomization

Randomization procedure

Randomization will be performed using a dedicated website and will be balanced per center. *Randomization arms*

Central randomization with the use of a permutated-block randomization list (block length 6) will be used. Participants will be allocated to the prone position or standard care on a 1:1 ratio. At each site, at least two investigators will be involved: one who will be aware of the allocated intervention and collect the data; the other will remain blinded to the interventions and evaluate the outcomes.

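### Section 8.2 states two thresholds for the final test of the primary outcome: P ≤ 0.044 from the group-sequential plan, and a general p-value of 0.05 that does not exempt it

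*Protocol*

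**What the plan says.** Section 6.4 fixes the design level, "assuming a twosided significance level of 0.05 and a power of 80"%.

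Section 8.2 then sets out a non-binding group-sequential design with gamma spending (gamma = -4 for alpha and for beta). Looks are given as 50% (N=357), 75% (N=476) and 100% (N=714), to be held as needed. The nominal P boundaries for efficacy, with futility in parentheses, "are P≤ 0.006 (P>0.82), P≤ 0.015 (P>0.35), and P ≤ 0.044 (P>0.044"). At the last look the two meet: P ≤ 0.044 is efficacy and P > 0.044 is futility. The primary effect is to be estimated by logistic regression with a 95% interval.

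The closing part of the same section states: "By definition, only the analysis of the primary outcome is confirmatory; all other analyses are exploratory". Shortly afterwards it gives the general rule: "Statistical significance is considered to be at a p-value of 0.05, where 95% confidence levels will express appropriate statistical uncertainty". This rule does not mention the boundaries, and it is not limited to the exploratory analyses.

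**The concern.** The two interim efficacy looks spend part of the 5%, which is why the final boundary is below 0.05. A general threshold of 0.05, placed in the paragraph that identifies the confirmatory analysis and carrying no exception, takes that adjustment back if it is applied to the final primary test. For a final P above 0.044 and up to 0.05, the protocol supports either conclusion. The choice would then be made after the result is known, and an analysis plan could follow either sentence and claim to comply. What is at stake is the single success criterion of the trial and, to a small extent, its 5% error rate.

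**Working it through.** **Inputs**
- Overall two-sided alpha 0.05 (section 6.4).
- Gamma spending with gamma = -4, futility non-binding, so it is ignored for type I error (section 8.2).
- Looks at information fractions 0.50, 0.75 and 1.00 as labelled. The stated N=476 gives 476/714 = 0.667, whereas 75% of 714 is 535.5. Both timings are run.
- 357 per arm, from "These calculations indicated that 322 patients would be required per group" plus 10% dropout, allocated 1:1 (sections 6.4 and 7.2.1).

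**Step 1. Reproduce the stated boundaries.** Cumulative two-sided alpha spent at fraction t is 0.05 × (1 − e^(4t)) / (1 − e^4).
- t = 0.50: 0.05 × 6.389/53.598 = 0.00596
- t = 0.75: 0.05 × 19.086/53.598 = 0.01780
- t = 1.00: 0.05

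Solving for the boundaries with the joint normal distribution of the z-statistics, where corr(Z_i, Z_j) = √(t_i/t_j) for t_i < t_j:

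| Second look | z boundaries | Nominal two-sided P |
|---|---|---|
| t = 0.75 | 2.750 / 2.432 / 2.012 | 0.0060 / 0.0150 / 0.0443 |
| t = 0.667 (N=476) | 2.750 / 2.586 / 2.000 | 0.0060 / 0.0097 / 0.0455 |

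The first row matches the protocol. The 0.044 is therefore a deliberate result of the spending function, and the stated set belongs to a true 75% look, not to N=476.

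**Step 2. Overall type I error under each final threshold.** Error = 1 − P(|Z1| < c1, |Z2| < c2, |Z3| < c3) under no effect, with c1 = 2.748 (P = 0.006), c2 = 2.432 (P = 0.015), and c3 = 2.014 (P = 0.044) or 1.960 (P = 0.05).

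| Second look | Final P ≤ 0.044 | Final P ≤ 0.05 |
|---|---|---|
| 75% | 0.0498 | 0.0552 |
| N=476 | 0.0508 | 0.0563 |

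If futility stops were always obeyed, the 0.05 rule would give about 0.053. With no interim efficacy look, a final 0.05 gives exactly 0.05.

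**Step 3. Can a result fall between the thresholds?** Take 115 of 357 events under standard care and 91 of 357 under prone position.
- Difference = 24/357 = 0.0672; pooled rate = 206/714 = 0.2885.
- z = 0.0672 / √(0.2885 × 0.7115 × 2/357) = 0.0672/0.0339 = 1.98, so P = 0.047.

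This is futility against the 0.044 boundary and significant at 0.05. At the planned control rate of 34% the zone is skipped: with 121 control events, 97 prone events give P = 0.051 and 96 give P = 0.042.

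**Step 4. The interval in the same example.** Odds ratio = (91/266)/(115/242) = 0.720, log −0.3286, standard error √(1/91 + 1/266 + 1/115 + 1/242) = 0.1661.
- 95%: exp(−0.3286 ± 1.960 × 0.1661) = 0.520 to 0.997.
- 95.6%, which matches P ≤ 0.044: exp(−0.3286 ± 2.014 × 0.1661) = 0.515 to 1.006.

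The ordinary 95% interval excludes 1 although the boundary is not crossed.

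**The case against.** The best defence is that the texts can be read together. Section 6.4 gives 0.05 as the overall level, the boundaries spend exactly that level, and a specific rule normally prevails over a general one. On that view the later 0.05 is boilerplate for the whole section. This is a reasonable reading, and probably what was meant. But the sentence words 0.05 as a p-value threshold rather than an overall level, follows the naming of the confirmatory analysis, and carries no exception. The reader has to supply the reconciliation.

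Three stronger readings are tempting and are not supported:
- *That the protocol sets the confirmatory test at 0.05.* The sentence does not name the primary outcome; it only fails to exempt it.
- *That the 95% interval is a further success rule.* No text makes it one. A conventional interval beside a sequential test is legitimate as description, so this is a reporting mismatch only.
- *That the error rate is badly compromised.* The excess is about half a percentage point and depends on the interim looks, which are held only as needed. Applying 0.05 at all three looks would give about 9.7%, but the explicit interim boundaries rule that out.

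It also stands that the zone is narrow: at 357 per arm and about 34% in the control group, no whole-patient result falls in it.

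That details may sit in a separate analysis plan does not remove the point. This is not a missing detail: the protocol states two incompatible values.

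**Conclusion.** The point holds as a contradiction in the decision threshold, with a small numerical effect. The final boundary of 0.044 is correctly derived for looks at 50%, 75% and 100%. The unrestricted 0.05 sentence conflicts with it for any final P above 0.044 and up to 0.05. Using 0.05 at the end raises the overall two-sided type I error from 5.0% to about 5.5%, or from 5.1% to 5.6% if the stated boundaries are used with the second look at N=476. These figures assume that both interim efficacy looks are held at the stated limits and that futility is non-binding. They vanish if no interim efficacy look takes place. The point merits correction because it concerns the only confirmatory test, not because the inflation is large.

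**What to change.** In section 8.2:
1. State that the primary outcome is judged only against the group-sequential boundaries: final P ≤ 0.044, or the limit recomputed from the gamma = -4 spending function for the looks actually held.
2. Reconcile the second look. Either the fraction or the N must change, because 476 is 66.7% of 714. For a look at N=476 the boundaries would be 0.0060 / 0.0097 / 0.0455.
3. Say that 0.05 is the overall two-sided level for the primary outcome and the nominal level for exploratory analyses only.
4. As a secondary reporting point, give an interval for the primary effect that matches the boundary (95.6% or sequentially adjusted), or state that the 95% interval is descriptive and does not decide success.

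The cost is a few sentences. The final threshold becomes slightly stricter than 0.05 when interim looks have been held. Sample size and trial conduct stay as they are, unless the second look is moved.
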